### **4.2 Inclusion Criteria for All Subjects**

Subjects must satisfy the following criteria to be enrolled in the study:

1. Male or female subjects 18 to 65 years of age, inclusive, at the time of signing the ICF.
2. Subject must understand and voluntarily sign an ICF prior to any study-related assessments/procedures being conducted.
3. Subject is willing and able to adhere to the study visit schedule and other protocol requirements.
4. Subject has a diagnosis of MS according to the 2017 revision of the McDonald diagnostic criteria and has RMS: RRMS or secondary progressive MS with active disease based on recent clinical relapse or MRI lesion activity ([Thompson, 2018](#))
5. At Screening, subjects must be on one of the following three treatment options and willing to remain on the same treatment for the duration of the study:
  - a. Treatment with ozanimod (0.92 mg maintenance dose). Ozanimod treatment must have been initiated at least █ days prior to the Day 1 Visit. Subjects should be compliant with the ozanimod label. In addition, in the █ days prior to Day 1, ozanimod treatment must not have been interrupted for more than 1 day.
  - b. Treatment with a non-pegylated form of IFN- $\beta$  and compliant with dosing within █ of Day 1 per the manufacturer's label
  - c. No treatment with a DMT for RMS
6. Subject is ambulatory (with or without walking aid) at Screening.
7. Subject is relapse-free in the 30 days prior to Day 1; during this period, subjects must have been clinically stable, without systemic corticosteroid or adrenocorticotropic hormone treatment.
8. Subjects who receive ozanimod or non-pegylated IFN- $\beta$  as their standard of care medication must do so in accordance with the local drug label.
9. Females of childbearing potential (FCBP) who receive ozanimod as their standard of care medication must agree to use contraception according to the approved local label.

All Subjects:

Periodic abstinence (calendar, symptothermal, post-ovulation methods), withdrawal (coitus interruptus), spermicides only, and lactational amenorrhoea method (LAM) are not acceptable methods of contraception. Female condom and male condom should not be used together.

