11. Subject has received any vaccine within 30 days prior to Day 1 including any SARS-CoV-2 (COVID-19) vaccine (first or second dose), or planned vaccines including COVID vaccine throughout the study period.
12. Subject has received any tetanus vaccine within 1 year prior to Screening.
13. Subject has received the seasonal influenza vaccine for the 2021/2022 influenza season prior to Day 1, or history of influenza vaccine for the 2020/2021 influenza season within 6 months prior to Day 1.

14. Subject has received PPSV23 within 5 years prior or PCV13 within 1 year of the Day 1.
15. For subjects receiving ozanimod: known contraindication against receiving ozanimod, according to product label.
16. For subjects on IFN- $\beta$ : known contraindication against IFN- $\beta$  or ongoing tolerability issues that might jeopardize compliance during the study (eg, injection site reactions requiring treatment, intolerable influenza-like symptoms, etc).
17. Subject has previous treatment with one of the following medications or interventions within the corresponding timeframe described as follows:
  - a. Previous treatment with lymphocyte-depleting therapies (eg, Campath®, anti-CD4, cladribine, cyclophosphamide, mitoxantrone, total body irradiation, bone marrow transplantation, stem cell transplantation, alemtuzumab, or daclizumab)
  - b. Previous treatment with teriflunomide within 8 months prior to randomization (unless teriflunomide plasma concentration is less than 0.02 mg/L [20 ng/mL]) or the subject had successfully followed the accelerated elimination procedure as described in the product label.
  - c. 180 Days prior to Day 1 or 5 half-lives, whichever is longer: any investigational agent or interventional therapy (excluding life-style interventions)
  - d. 180 Days prior to Day 1: azathioprine, methotrexate, cyclosporine, mycophenolate anti-CD20 mAbs (including rituximab, ocrelizumab, ofatumumab), Bruton's tyrosine kinase (BTK) inhibitors. After discontinuation of anti-CD20 mAbs, subjects must have documentation of ALC and gamma globulin levels within the normal range.
  - e. 60 Days prior to Day 1: fingolimod, dimethyl fumarate
  - f. Subjects who discontinued an S1P modulator due to lymphopenia must have a documented ALC  $>0.2 \times 10^9/L$  within 6 months prior to baseline and for subjects on ozanimod, documented after a minimum of [redacted] days of treatment with ozanimod.

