### **Post-vaccination**

After vaccination, subjects should be observed for approximately 15 minutes, or as per recommended local guidelines, whichever is longer, for development of hypersensitivity reactions. Should hypersensitivity reactions occur, the Investigator should record the event as an AE and should monitor pulse and blood pressure. The Investigator must determine if treatment with steroid, antihistamines, epinephrine/adrenaline, or hospital admission is warranted and act accordingly. If no hypersensitivity reactions develop or a mild to moderate hypersensitivity reaction has stabilized, subjects can leave the site. Subjects should be informed that over the counter ibuprofen or acetaminophen (paracetamol) can be used to treat post-vaccination pain or fever, but subjects should refrain from using anti-pyretic treatments, including acetaminophen, aspirin, and other NSAIDs for a minimum of 6 hours post-vaccination ([Scheifele, 2018](#); [Doedee, 2014](#)).

Vaccine administration must conform with the label requirements and must be performed by someone who is experienced in intramuscular and subcutaneous administration of medicinal products. Sites must have epinephrine or adrenaline medication available that can be administered in case of anaphylactic reactions. Subjects should be stably seated or reclined before and during vaccine administration to avoid injuries from falls or in case of syncopal reactions. Standard hygiene practices should be applied during vaccine administration, including skin disinfection with alcohol swaps at the site of vaccine administration and hand cleaning or wearing gloves by the person administering the vaccine. The seasonal influenza vaccine and Tdap must be administered intramuscularly, and PPSV23 should be administered subcutaneously. The recommended anatomical site of administration for each vaccine is listed in [Table 4](#). Only one vaccine must be administered per anatomical site. On the day that the vaccine is administered, subjects who receive IFN- $\beta$  injections must not have IFN- $\beta$  administered at a site of vaccine administration.

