### **9.1 Overview**

This is a non-randomized, open-label study in which all subjects remain on their pre-study (baseline) treatment per protocol. Subjects will be recruited by investigators from MS clinical practice patients and prospectively assessed for immune response to vaccination. The statistical analyses will focus on estimating immune response rates, adjusting for baseline subject-level characteristics. No formal statistical hypothesis is evaluated. To mitigate for potential differences in the recruited subject population in the ozanimod and non-ozanimod arms that potentially could affect immune response, response rates will be estimated based on a logistic regression model adjusting for several factors, eg, age, sex, body mass index (BMI), and baseline absolute lymphocyte count (ALC). The results of the statistical analyses for immune response endpoints will be summarized for subjects receiving ozanimod (ozanimod arm) and subjects not receiving ozanimod (non-ozanimod arm) as their standard of care disease modifying therapy for MS. Analyses of safety will be summarized by descriptive statistics separately for the ozanimod and non-ozanimod arms.

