### **9.3 Sample Size and Power Considerations**

The sample size of the study is 60 subjects with an estimated 30 subjects expected to have received ozanimod and 30 subjects expected to not have received ozanimod as standard of care DMT. It is expected that approximately 60% of the subjects not receiving ozanimod as standard of care therapy will have a serologic response to vaccination with Tdap ([Kappos, 2015](#)).

With a sample size of 30 subjects for the ozanimod arm, assuming the response rate is 45%, the expected half width of the 95% confidence interval (based on normal approximation) is approximately 0.175. We note that in simulations (assuming a true response rate of 0.45), the estimated response rate falls within 0.267 and 0.633 among 95% of the simulated trials (across 100,000 simulations).

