## **9.7 Safety Analysis**

All subjects who receive at least 1 vaccine, the mITT population, will be included in the safety analyses. Adverse events will be summarized by worst severity grade. Adverse events, with particular focus on treatment-emergent AEs, will be summarized by MedDRA system organ class, and preferred term. This will include vaccine-related adverse events, adverse events leading to death or to discontinuation from treatment, serious adverse events, and events of interest.

Associated laboratory parameters such as hepatic enzymes, renal function, and hematology values will be grouped and presented together. Individual subject values will be listed and values outside of the standard reference range will be flagged. Shift tables and analyses of changes from baseline will be produced. The change from baseline for blood pressure monitoring, each of the vital signs and physical examination parameters will be summarized. The incidence of abnormal vital signs parameters and outlier physical examination results will be tabulated.

By-subject listings will be provided for all relevant safety data. Graphical displays and figures will be provided where useful to assist in the interpretation of results.

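### Safety tables pool IFN-beta and untreated controls, so IFN-beta background reactions can mask poorer vaccine tolerability on ozanimod

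*Combined protocol and SAP*

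**What the plan says.** Safety and tolerability is a secondary objective (Section 2, Table 1). Section 9.1 sets the groups: "Analyses of safety will be summarized by descriptive statistics separately for the ozanimod and non-ozanimod arms". The comparator is defined by exclusion, as "subjects not receiving ozanimod (non-ozanimod arm) as their standard of care disease modifying therapy for MS". Under inclusion criterion 5 in Section 4.2 it takes in both users of non-pegylated IFN-beta and those with "No treatment with a DMT for RMS". Section 9.3 plans for "30 subjects expected to not have received ozanimod as standard of care DMT", and neither it nor Section 4.1 sets a target, minimum or cap for either kind of control.

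Section 9.7 fixes the population: "All subjects who receive at least 1 vaccine, the mITT population, will be included in the safety analyses". Of the event summaries it says "This will include vaccine-related adverse events". It also promises by-subject listings. It describes no split of the controls.

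Sections 1.3.3 and 1.3.4 support IFN-beta as a control by citing antibody responses similar to those of untreated subjects. Nothing comparable is offered for adverse events. Exclusion criterion 16 (Section 4.3) removes IFN-beta users with ongoing tolerability problems that could threaten compliance, giving as examples "injection site reactions requiring treatment, intolerable influenza-like symptoms". Section 7.2 says that, on the day of vaccination, IFN-beta must not be "administered at a site of vaccine administration".

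**The concern.** Similar antibody responses are a reason to pool the two kinds of control for immunogenicity. They are no reason to pool them for tolerability. Criterion 16 shows that the authors know IFN-beta produces injection-site and influenza-like reactions, and subjects whose reactions do not threaten compliance still enter.

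IFN-beta continues on its usual schedule during follow-up. The regimens in Section 1.2 imply about 28/7 = 4 injections (weekly), 3 x 4 = 12 (three times a week) or 28/2 = 14 (every other day) over 28 days, against two or three vaccine injections. The rule that keeps IFN-beta away from vaccine sites covers the vaccination day only.

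The same AE terms can therefore arise from two sources in some controls and from one source in the others. The pooled rate would then depend partly on how many IFN-beta users happen to be recruited. Section 1.3.1 says the data will support the ozanimod labels. If ozanimod subjects tolerate the vaccines less well than untreated subjects do, a pooled control rate lifted by IFN-beta could make the two arms look alike.

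**Working it through.** **The plan's own figure.** The documents give no precision figure for safety. The only one, in Section 9.3, concerns immune response: an expected 95% half-width of about 0.175 for n = 30 and a rate of 0.45. It reproduces. The plug-in value is 1.96 x sqrt(0.45 x 0.55 / 30) = 0.178, and the expectation over the binomial distribution is 0.1749.

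**Inputs for the safety question.** None of these is in the documents; all are assumptions.
- p0, event rate in no-DMT controls: 0.30
- d, excess event rate on IFN-beta: 0 to 0.30
- s, IFN-beta share of the controls: 0.25 to 0.75
- e, true excess on ozanimod over no DMT: 0.15, so the ozanimod rate is 0.45. That it equals the immune-response rate assumed in Section 9.3 is a coincidence.

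**Formulas.** Pooled control rate = (1 - s) x p0 + s x (p0 + d) = p0 + s x d. Apparent ozanimod excess = (p0 + e) - (p0 + s x d) = e - s x d. The bias is s x d and does not depend on p0.

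| s | d | s x d | Pooled control rate | Apparent excess (true 0.15) |
|---|---|---|---|---|
| any | 0 | 0 | 0.30 | +0.15 |
| 0.25 | 0.10 | 0.025 | 0.325 | +0.125 |
| 0.50 | 0.10 | 0.05 | 0.35 | +0.10 |
| 0.50 | 0.20 | 0.10 | 0.40 | +0.05 |
| 0.50 | 0.30 | 0.15 | 0.45 | 0 |
| 0.75 | 0.30 | 0.225 | 0.525 | -0.075 |

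At the top of the range the true excess is cancelled or reversed. With d near zero nothing happens.

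**What a split costs in precision.** The 95% half-width for a difference of 0.45 (30 ozanimod subjects) versus 0.30 (m controls) is 1.96 x sqrt(0.45 x 0.55/30 + 0.30 x 0.70/m):
- m = 30: 1.96 x sqrt(0.00825 + 0.00700) = 0.242
- m = 15: 1.96 x sqrt(0.00825 + 0.01400) = 0.292
- m = 8: 1.96 x sqrt(0.00825 + 0.02625) = 0.364

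Even the largest bias in the table, 0.225, is smaller than the half-width with all 30 controls. The split columns can show where events come from. They cannot settle a difference.

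**The case against.** The strongest reply is that the plan already filters out most IFN-beta background.
- Section 10.1 counts an event only if it appears or worsens on study, and IFN-beta users enter already treated and clinically stable.
- Criterion 16 removes problems that might jeopardise compliance. It should not be read as removing severe reactions only: its examples are open-ended and include site reactions that merely need treatment.
- Section 10.2.3 lets the investigator attribute an event to another medicine, and Section 9.7 tabulates vaccine-related AEs and lists all relevant safety data by subject.
- No hypothesis is tested, and safety is summarised separately by arm, so no tolerability conclusion is pre-specified.

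Much of this stands. A reader might infer that the control rate is in fact inflated. The documents do not support that: they give no AE rate by control type and no IFN-beta share, and the new-or-worsening rule makes a small excess plausible.

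The filters are nevertheless incomplete. IFN-beta symptoms can recur after each injection. The only scheduled post-vaccination visit is at Day 28, and no diary or solicited-event schedule is described, so telling an unchanged symptom from a new one may rest largely on recall. Causality is judged open-label, and IFN-beta is an alternative explanation available for some controls and not for others. That could push the vaccine-related table in either direction. Listings allow later reconstruction but are not a planned summary.

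A reader might also infer that the no-DMT subjects are the one clean reference. That is not supported either: they are not randomised, may differ in why they are untreated, and may be very few.

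**Conclusion.** The point holds as a possibility that the planned tables cannot reveal. The documents establish the two-group safety summary, the unplanned mix of controls, a rationale for the IFN-beta control that covers antibody response only, and recognised IFN-beta reactions that overlap with vaccine reactions. Masking is possible and has not been shown to occur. Its size is s x d, from 0 to 0.225 over the assumed ranges, and those ranges are illustrations, not estimates.

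No test or decision rule is affected. It also cannot be said that the controls will never be shown separately, because Section 9 defers detailed methods to a separate SAP whose text is not in the document supplied. The protocol itself describes no split. This is an inexpensive improvement in how the safety data are displayed and does not affect the study's validity.

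**What to change.** In Sections 9.1 and 9.7, and in the SAP:
- Show the AE and vaccine-related AE tables, at least for influenza-like and injection-site terms, with columns for ozanimod, IFN-beta, no DMT and pooled non-ozanimod. The pooled column stays.
- For those terms, give onset day relative to vaccination.
- State that any ozanimod-versus-control tolerability statement will be interpreted in light of the split columns, with their denominators and uncertainty shown, and will not rest on the no-DMT column alone.

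The argument concerns reactions that IFN-beta and vaccines share, so it gives no reason to split the relapse summaries.

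The cost is two extra table columns and one derived variable. DMT status and AE start dates are already collected, so there is no new data collection. The drawback is small cells: at the assumed rates the half-width for a difference is about 0.29 with 15 controls and 0.36 with 8, against 0.24 with all 30.

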### **9.2 Study Population Definitions**

The study will include two cohorts differentiated by the vaccines administered. Cohort 1 comprises subjects who receive Tdap, PPSV23, and the seasonal inactivated influenza vaccine. Cohort 2 comprises subjects who receive Tdap and PPSV23 only. Initiation of Cohort 2 will be based on the availability of eligible subjects who have not previously been vaccinated with the seasonal inactivated influenza vaccine.

The modified intent-to-treat (mITT) population consists of all subjects who received at least one vaccination and summarized according to their initial treatment status (ozanimod vs. non-ozanimod) regardless of systemic use of corticosteroids.

The per-protocol (PP) population consists of all subjects who received the correctly assigned vaccinations, had no steroid use, and did not receive any other vaccines throughout the study.

### **9.3 Sample Size and Power Considerations**

The sample size of the study is 60 subjects with an estimated 30 subjects expected to have received ozanimod and 30 subjects expected to not have received ozanimod as standard of care DMT. It is expected that approximately 60% of the subjects not receiving ozanimod as standard of care therapy will have a serologic response to vaccination with Tdap ([Kappos, 2015](#)).

With a sample size of 30 subjects for the ozanimod arm, assuming the response rate is 45%, the expected half width of the 95% confidence interval (based on normal approximation) is approximately 0.175. We note that in simulations (assuming a true response rate of 0.45), the estimated response rate falls within 0.267 and 0.633 among 95% of the simulated trials (across 100,000 simulations).

#### **9.4 Background and Demographic Characteristics**

The following summaries will be provided by treatment status (ozanimod vs non-ozanimod) based on the mITT population:

Subject's age, height, weight, and baseline characteristics will be summarized using descriptive statistics, while sex, race and other categorical variables will be provided using frequency tabulations. Medical history data will be summarized using frequency tabulations by Medical Dictionary for Regulatory Activities (MedDRA) system organ class and preferred term.

#### **9.5 Subject Disposition**

The following summaries will be provided by treatment status (ozanimod vs non-ozanimod) based on the mITT population.

The number and percentage of subjects will be summarized. Subject disposition, including the number of subjects who enrolled, completed the trial, and discontinued the trial with reasons for discontinuation. Subject demographics include age, sex, race, ethnicity, height, weight, and body mass index.

Baseline characteristics include age at MS symptom onset, age at MS diagnosis, years since MS symptom onset, years since MS diagnosis, number of relapses within the last 12 months, number of relapses within the last 24 months, and number of GdE lesions.

#### **9.6 Immune Response Analysis**

The primary endpoint analysis and all analyses for immune-response to vaccination will be performed in the per-protocol population, ie, in subjects who received the correctly assigned vaccinations and had no major protocol violations. Sensitivity analyses will be conducted within the mITT population consisting of all subjects who received at least one vaccination and summarized according to their initial treatment status (ozanimod vs non-ozanimod) regardless of protocol violations

If Cohort 2 is initiated, then not all subjects will receive the seasonal inactivated influenza vaccine. For the purposes of summarizing the Tdap and PPSV23 vaccines, all subjects in Cohorts 1 and 2 will be combined, since they generally would have had the opportunity to receive all three vaccines. For evaluating the seasonal inactivated influenza vaccine, the analyses will be based on Cohort 1 subjects.

The ozanimod and non-ozanimod treatment group immune response rates and differences will be estimated based on a model adjusting for baseline demographics (eg, age, gender, BMI, baseline ALC, etc). We note the estimates of treatment differences should be interpreted with caution, since, in addition to the limited sample size, the ozanimod and non-ozanimod arms are not randomized. Some or all of the aforementioned factors may not be feasible to include in the analysis model. Analysis details will be provided in the statistical analysis plan such as the required number of subjects within each factor stratum (eg, if within a factor stratum level there are less than 10 subjects, then that factor will be excluded from the model).

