### **1.3.6      *Rationale for Selected Endpoints***

#### **Primary Endpoint**

**Tetanus Toxoid Immune Response** - The proportion of subjects with serologic response to tetanus toxoid in the Tdap vaccine will serve as the primary endpoint in this study. Serologic response to tetanus toxoid is measured by comparing the anti-tetanus toxoid IgG antibody titers at 4 weeks post-vaccination compared to the pre-vaccination titers. The antibody titers will be measured by an ELISA method. Subjects with a pre-vaccination IgG antibody titer level  $\leq 0.10$  IU/mL will have a serologic response if post-vaccination titer levels are  $\geq 0.40$  IU/mL. To demonstrate a serologic response if pre-vaccination titer levels are  $> 0.10$  IU/mL and  $\leq 2.7$  IU/mL, subjects will have at least a 4-fold increase in post-vaccination titers. If subjects have a pre-vaccination titer level  $> 2.7$  IU/mL, they will have at least a 2-fold increase in titers to demonstrate a response. This endpoint is supported by the recommendations to manufacturers of tetanus vaccines to establish immune response which stipulates 0.10 IU/mL as a seroprotective level against tetanus and establishes increased Ab titers needed to demonstrate immune response based on pre-vaccination titer level ([WHO Technical Report Series, No. 980, Annex 5](#)). The requirement for a serologic response above the upper baseline level of 2.7 IU/mL as a 2-fold increase is supported by the WHO recommendations to establish tetanus vaccine efficacy, as well as by research demonstrating subjects with higher baseline titers are associated with less than a 4-fold response to vaccination ([Petras, 2018](#); [Halperin, 2018](#)). Assessing the tetanus toxoid vaccine immune response at 4 weeks is also recommended by the [WHO Technical Report Series, No. 980, Annex 5](#) and coincides with peak humoral immune response in adults ([Blatter, 2009](#)).

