**Diphtheria Toxoid Immune Response** - The proportion of subjects with serologic response to the diphtheria toxoid in the Tdap vaccine will be assessed in this study. Serologic response to diphtheria toxoid is measured by comparing the IgG anti-diphtheria antibody titers at 4 weeks post-vaccination to the pre-vaccination titers. The antibody titers will be measured by ELISA. Subjects with a pre-vaccination IgG antibody titer level of  $\leq 0.10$  IU/mL will have a serologic response if post-vaccination levels are  $\geq 0.40$  IU/mL. To demonstrate a serologic response if pre-vaccination titer levels are  $> 0.10$  IU/mL and  $\leq 2.56$  IU/mL, subjects will have at least a 4-fold increase in post-vaccination titers. If subjects have a pre-vaccination titer  $> 2.56$  IU/mL, they will have at least a 2-fold post-vaccination increase in titers to demonstrate a response. This endpoint to assess diphtheria vaccine response is supported by the recommendations to manufacturers of diphtheria vaccines ([WHO Technical Report Series, No. 980, Annex 4](#)) which stipulates 0.10 IU/mL as a seroprotective level against diphtheria and established the demonstration of the increased Ab titers needed to demonstrate immune response based on pre-vaccination titer level. The use of an upper baseline level above which a 2-fold increase is required to demonstrate serologic response is supported by the WHO recommendations to establish diphtheria as well vaccine efficacy and by research that demonstrates subjects with higher baseline diphtheria titers are associated with less than a 4-fold increase in titers ([Halperin, 2018](#)).

Additional secondary endpoints to assess diphtheria vaccine serologic response are the proportion of subjects with anti-diphtheria toxoid IgG  $\geq 0.1$  indicative of seroprotection, and the GMC ratio of pre- and post-vaccination anti-diphtheria toxoid IgG and IgM titers.

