**Table 2:** **Study Endpoints**

Endpoint	Name	Description	Time frame
Primary	Proportion of subjects with serologic response to tetanus toxoid	Serologic response to tetanus toxoid:  If pre-vaccination antibody titer is $\leq 0.10$ IU/mL, post-vaccination level $\geq 0.40$ IU/mL; if pre-vaccination antibody titer is $> 0.10$ IU/mL and $\leq 2.7$ IU/mL, at least a 4-fold increase in titer; if pre-vaccination antibody titer is $> 2.7$ IU/mL, at least a 2-fold increase in titer	At the Day 28 post-vaccination visit

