**Table 2:** **Study Endpoints**

Endpoint	Name	Description	Time frame
	GMC ratio of anti-tetanus toxoid IgG	The ratio of the geometric mean of the post-vaccination anti-tetanus toxoid IgG concentration (at the post vaccination day 28 visit) divided by the geometric mean of the pre-vaccination anti-tetanus toxoid IgG concentration	At the Day 28 post-vaccination visit
	GMC ratio of anti-tetanus toxoid IgM	The ratio of the geometric mean of the post-vaccination anti-tetanus toxoid IgM concentration (at the post vaccination day 28 visit) divided by the geometric mean of the pre-vaccination anti-tetanus toxoid IgM concentration	At the Day 28 post-vaccination visit
	GMC ratio of anti-pneumococcus IgG for each pneumococcal serotype in PPSV23	The ratio of the geometric mean of the post-vaccination anti-pneumococcus IgG concentration (at the post vaccination day 28 visit) divided by the geometric mean of the pre-vaccination anti-pneumococcus IgG concentration. To be calculated separately for each pneumococcal serotype.	At the Day 28 post-vaccination visit

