## 6.2 Treatment Period - Day 1/Baseline

The following evaluations will be performed at the frequency specified in [Table 3](#). The evaluations should be performed prior to vaccine administration on Day 1, unless otherwise specified.

- Review of subject eligibility
- Confirmation and source documentation by the PI that subjects have taken ozanimod or IFN- $\beta$  as prescribed by the manufacturer label and as required in the inclusion criteria
- Concomitant medications evaluation
- AE evaluation
- Urine pregnancy test confirmed negative for pregnancy
- Vital signs (including blood pressure, temperature, and heart rate)
- Symptom oriented physical examination
- Urinalysis and blood sampling for the follow laboratory tests:
  - Serologic antibody testing for COVID-19 and other PD parameters
  - Hematology: red blood cell (RBC) count, total and differential white blood cell (WBC) count (basophils, eosinophils, lymphocytes, monocytes, and neutrophils), platelet count, hemoglobin, hematocrit, mean corpuscular volume (MCV), mean corpuscular hemoglobin (MCH), and mean corpuscular hemoglobin concentration (MCHC).
  - Blood Chemistry: sodium, potassium, chloride, calcium, magnesium, phosphate, blood urea nitrogen, glucose, albumin, alkaline phosphatase, creatinine, alanine aminotransferase (ALT) (SGPT), aspartate aminotransferase (AST) (SGOT), gamma-glutamyl transferase (GGT), total bilirubin, and conjugated bilirubin. Abnormal laboratory parameters inconsistent with clinical presentation of MS or suspicious of underlying medical condition should be repeated for accuracy.
- Efficacy assessments, including blood draw for pre-vaccination antibody titer determination, and blood draw for PK (see [Section 6.4](#))
- Administration of Tdap, PPSV23, and influenza vaccine (Cohort 1 only), (intramuscularly or subcutaneously, as described in [Table 4](#) )

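### Pre-vaccination titre, which sets the tetanus response threshold, is not among the example covariates for the adjusted arm comparison and should be named, with its role stated

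*Combined protocol and SAP*

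**What the plan says.** The adjustment model is described in four places: Protocol Summary (Statistical Methods), Section 1.3.4, Section 9.1 and Section 9.6. Section 9.6 has "a model adjusting for baseline demographics (eg, age, gender, BMI, baseline ALC, etc"). All four give age, sex or gender, BMI and baseline ALC, always as examples. Section 9.6 adds that some or all of these may prove infeasible, that a factor with a sparse stratum may be dropped (fewer than 10 subjects is the example), and that details will be in the SAP. No separate SAP text is in the documents supplied. Section 9.5 lists baseline characteristics to summarise; titre is not among them.

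Elsewhere the protocol treats titre as central:

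- Table 2 scores tetanus response by pre-vaccination level: at or below 0.10 IU/mL, a post-vaccination level of at least 0.40 IU/mL; above 0.10 and up to 2.7 IU/mL, "at least a 4-fold increase in titer"; above 2.7 IU/mL, a 2-fold increase.
- Section 1.3.6 supports the 2-fold tier by citing "research demonstrating subjects with higher baseline titers are associated with less than a 4-fold response to vaccination", and says for diphtheria that "subjects with higher baseline diphtheria titers are associated with less than a 4-fold increase in titers".
- Section 6.2 schedules a "blood draw for pre-vaccination antibody titer determination" on Day 1.
- The exploratory tetanus GMC ratio is "divided by the geometric mean of the pre-vaccination anti-tetanus toxoid IgG concentration", so the baseline geometric mean is already needed.

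**The concern.** Section 9.1 gives the model's purpose: to mitigate differences between self-selected arms that could affect immune response. The baseline value that the protocol itself connects most directly with response is not in the example list, and Section 9.6 labels the list demographics, a term that would not normally cover an antibody titre.

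The eligibility criteria do not settle the matter. One exclusion reads "Subject has received any tetanus vaccine within 1 year prior to Screening". It removes recent boosters but does not equalise titre among subjects vaccinated at different times before that.

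At stake is the adjusted arm difference for the primary endpoint and for the other serologic-response endpoints. Section 1.3.1 says the data will support the ozanimod labels. A bias from titre imbalance would not be reflected in the confidence interval, and without a baseline row by arm in the planned summaries a reader might not see the imbalance.

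**Working it through.** **1. The plan's own figure.** Section 9.3: 30 subjects on ozanimod, response rate 45%.

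- Plug-in half-width: 1.96 × √(0.45 × 0.55 / 30) = 0.178. Averaged over Binomial(30, 0.45) it is 0.1749, matching the stated 0.175.
- Binomial 2.5% and 97.5% points: 8/30 = 0.267 and 19/30 = 0.633, as stated.

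These figures are not in dispute. For a difference, taking 45% against 60%: 1.96 × √(0.45 × 0.55/30 + 0.60 × 0.40/30) = 0.250. The 45% is used in Section 9.3 only for single-arm precision, so the 15-point gap is an assumption here.

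**2. Does the tiered rule already remove the dependence on titre?** One 4-fold threshold covers 0.10 to 2.7 IU/mL, a span of 2.7/0.10 = 27-fold. Let x be log2 pre-vaccination titre and let log2 fold-rise be a + b·x plus normal error with SD s. Then

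P(response | x) = 1 − Φ((need − a − b·x)/s),

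where need = log2(0.40) − x in the lowest tier, 2 in the middle tier and 1 in the top tier. With baseline GMC 1 IU/mL, SD of x 1.5, b = −0.5, s = 1.2 and a set to give 60% response overall, response falls from 0.94 just above 0.10 to 0.33 at 2.7, then jumps to 0.65 just above 2.7. The 2-fold tier corrects only in part.

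**3. Size of the effect.** The documents give no titre distribution, slope or residual SD, so every such input is assumed: SD of x 1.5, GMC 0.3 to 2 IU/mL, b from 0 to −0.7, s from 1.2 to 2.0. The intercept a is set per arm to give 45% and 60% at a common titre distribution. The ozanimod mean of x is then raised by 0.5 (1.4-fold) or 1.0 (2-fold). The effect is the raw difference minus the difference standardised to the pooled titre distribution. For s = 1.2, range over GMC, in percentage points:

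| Slope b | 1.4-fold higher | 2-fold higher |
|---|---|---|
| 0 | +1.9 to +4.1 | +4.0 to +8.2 |
| −0.1 | +0.5 to +2.6 | +1.1 to +5.2 |
| −0.2 | −1.0 to +1.0 | −1.9 to +2.0 |
| −0.3 | −2.6 to −0.6 | −5.0 to −1.2 |
| −0.5 | −5.5 to −3.5 | −10.7 to −7.0 |
| −0.7 | −7.7 to −5.8 | −15.2 to −11.5 |

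With s = 1.5 or 2.0 the −15.2 shrinks to −12.9 or −10.2. If the ozanimod arm has the lower titre, the signs reverse.

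**4. Chance imbalance.** SD of the mean difference in x: 1.5 × √(2/30) = 0.387. P(at least 0.5 either way) = 0.197; P(at least 1.0) = 0.010.

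**5. With and without titre in the model.** Simulation used 3,000 trials of 30 + 30 per setting, slopes −0.3 and −0.7 only, s = 1.2, titre as confounder, logistic regression standardised to a risk difference.

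- With age, sex, BMI and ALC only, bias was 0.3 to 7.4 points in absolute size at 1.4-fold and 0.9 to 14.8 at 2-fold.
- With one log-titre term added, bias lay between −0.3 and +1.2 points throughout.
- Adding titre changed the variance by −17% to +3% with balanced arms and by −21% to +13% at 2-fold. The worst RMSE penalty was about 1 point (16.0 to 16.9); the largest gain was 22.1 to 14.6.

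A separate large-sample check assumed no true effect, s = 1.5 and slope −0.5, with titre entered flexibly. It gave spurious differences of −0.035 and −0.070 at 1.4-fold and 2-fold without titre, and 0.001 and −0.003 with it.

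**6. Model size.** Expected non-responders: 30 × 0.55 + 30 × 0.40 = 28.5. Per parameter: 28.5/5 = 5.7 for arm plus four covariates; 28.5/6 = 4.75 with titre added.

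**The case against.** The strongest reply is that no four-covariate model has been fixed. Every list is illustrative, and Sections 9 and 9.6 leave the details to the SAP. That stands. A reader might infer that titre will be left out of the analysis, but the documents show only that it is not named.

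Second, bias presupposes confounding. Subjects are on their therapy before baseline: "Ozanimod treatment must have been initiated at least" a set number of days before Day 1. If therapy itself alters titre, omitting titre gives a total effect free of this bias, and including it gives a direct effect. This also stands, and it is why the role of titre needs stating.

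Third, size and sign depend on the chosen inputs. Near slope −0.2 the tiers roughly cancel the effect, and with flatter slopes it reverses. A reader might infer a bias against ozanimod of up to 15 points. That takes the steepest slope, the smallest residual SD and a 2-fold imbalance with about 1% probability by chance, and the documents report no imbalance and give no reason to expect one.

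Fourth, no hypothesis is tested, and Section 9.6 already asks for caution over sample size and non-randomisation. This limits the consequence. That caution is general, however, and it neither displays titre nor adjusts for it.

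**Conclusion.** The point holds as a conditional gap in pre-specification. Titre enters the endpoint rule, is linked by the protocol to fold-rise and is already measured, yet it is absent from all four example lists and from the baseline summary. Bias in the arm difference requires three things together: the arms differ in titre, titre is a confounder rather than a consequence of therapy, and the final model uses only the named factors.

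Under the assumed ranges, a 1.4-fold higher ozanimod titre shifts the unadjusted difference by about −8 to +4 points, and a 2-fold higher titre by about −15 to +8. The true size and sign cannot be known from the documents. Against a half-width of about 25 points the effect may be negligible; at the extreme it matches the assumed 15-point gap. This is a worthwhile, inexpensive improvement to an estimation study, not a flaw that invalidates it.

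**What to change.** In Section 9.6 and the SAP:

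- Name continuous log pre-vaccination antigen-specific IgG as a covariate in each serologic-response model (anti-tetanus IgG for the primary endpoint).
- State that the example rule on fewer than 10 subjects per stratum does not apply to it, because it is continuous.
- Report the arm difference with and without titre. Say whether titre is regarded as a confounder or as possibly affected by therapy, and that in the latter case the two estimates have different targets.

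In Section 9.5, tabulate baseline titre by arm: GMC and the share at ≤0.10, >0.10 to 2.7 and >2.7 IU/mL for tetanus.

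No new data are needed. The cost is SAP wording, a small addition to the baseline table and one more model parameter (4.75 instead of 5.7 expected non-responders per parameter), with slightly higher variance in some settings. The single log term was checked in trial-size simulation only at slopes −0.3 and −0.7.
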